APPENDIX II: UNACCEPTABLE ENZYME INDUCING AND RECOMMENDED NON-ENZYME INDUCING ANTICONVULSANTS

Recommended Non-enzyme inducing anticonvulsants
Clonazepam
Diazepam
Ethosuximide
Ezogabine
Gabapentin
Lacosamide
Lamotrigine
Levetiracetam
Lorazepam
Perampanel
Tiagabine
Topiramate
Valproic Acid
Zonisamide
Unacceptable Enzyme inducing anticonvulsants
Carbamazepine
Felbamate
Phenobarbital
Fosphenytoin
Phenytoin
Primidone
Oxcarbazepine

APPENDIX IV: PATIENT DIARY: RADIATION PHASE

COG Patient ID: _____ Institution : _____ Please do not write patient names on this form.

Complete each day with the time and dose of AZD1775 (MK-1775) given, and circle AM or PM. If a dose is not due or is accidentally skipped leave that day blank. ***Make note of other drugs and supplements taken under the Comments section below.*** If you vomit after taking the medication, the dose will not be repeated. Add the dates to the calendar below and return the completed diary to your institution each week. Your institution will upload this document into RAVE weekly. Refer to [Appendix V-B](#) for scheduling guidelines based on the day of the week XRT is initiated.

EXAMPLE					Number of capsules			Comments
WEEK 1	Date	Time		10 mg	25 mg	100 mg		
Day 1: MONDAY	1/15/14	8:30	AM		2	1	He felt nauseated an hour after taking the drug but did not vomit.	
Cycle #: _____		Dose: _____		Start Date: / / / / /		End Date: / / / / /		
WEEK 1		Date	Time		10 mg	25 mg	100 mg	Comments
Day 1:			AM/ PM					
Day 2:			AM/ PM					
Day 3:			AM/ PM					
Day 4:			AM/ PM					
Day 5:			AM/ PM					
Day 6:			AM/ PM					
Day 7:			AM/ PM					
WEEK 2		Date	Time		10 mg	25 mg	100 mg	Comments
Day 8:			AM/ PM					
Day 9:			AM/ PM					
Day 10:			AM/ PM					
Day 11:			AM/ PM					
Day 12:			AM/ PM					
Day 13:			AM/ PM					
Day 14:			AM/ PM					
WEEK 3		Date	Time		10 mg	25 mg	100 mg	Comments
Day 15:			AM/ PM					
Day 16:			AM/ PM					
Day 17:			AM/ PM					
Day 18:			AM/ PM					
Day 19:			AM/ PM					
Day 20:			AM/ PM					
Day 21:			AM/ PM					

COG Patient ID: _____

Institution : _____

Please do not write patient names on this form.

THIS PROTOCOL IS FOR RESEARCH PURPOSES ONLY, SEE PAGE 1 FOR USAGE POLICY

WEEK 4	Date	Time	10 mg	25 mg	100 mg	Comments
Day 22: _____		AM/ PM				
Day 23: _____		AM/ PM				
Day 24: _____		AM/ PM				
Day 25: _____		AM/ PM				
Day 26: _____		AM/ PM				
Day 27: _____		AM/ PM				
Day 28: _____		AM/ PM				
WEEK 5	Date	Time	10 mg	25 mg	100 mg	Comments
Day 29: _____		AM/ PM				
Day 30: _____		AM/ PM				
Day 31: _____		AM/ PM				
Day 32: _____		AM/ PM				
Day 33: _____		AM/ PM				
Day 34: _____		AM/ PM				
Day 35: _____		AM/ PM				
WEEK 6	Date	Time	10 mg	25 mg	100 mg	Comments
Day 36: _____		AM/ PM				
Day 37: _____		AM/ PM				
Day 38: _____		AM/ PM				
Day 39: _____		AM/ PM				
Day 40: _____		AM/ PM				
Day 41: _____		AM/ PM				
Day 42: _____		AM/ PM				

Notes: _____

THIS PROTOCOL IS FOR RESEARCH PURPOSES ONLY, SEE PAGE 1 FOR USAGE POLICY

APPENDIX V-A: AZD1775 (MK-1775) DOSING NOMOGRAM**AZD1775 (MK-1775) Dose Assignment: 50 mg/m²/day*
(Dose Levels -1, 1, 2, and 3)**

BSA (m ²)	Total Daily Dose (mg/day)
0.35-0.44	20
0.45-0.54	25
0.55-0.64	30
0.65-0.74	35
0.75-0.84	40
0.85-0.94	45
0.95-1.04	50
1.05-1.14	55
1.15-1.29	60
1.30-1.44	70
1.45-1.60	75
1.61-1.84	85
1.85-2.14	100
2.15- ≥ 2.30	110

*Dose Level -1: Days 1, 3, 5, 15, 17, 19, 29, 31, 33

Dose Level 1: Days 1-5, 15-19, 29-33

Dose Level 2: Days 1-5, 8, 10, 12, 15-19, 22, 24, 26, 29-33, 36, 38, 40

Dose Level 3: Days 1-5, 8-12, 15-19, 22-26, 29-33, 36-40

Refer to [Appendix V-B](#) for scheduling guidelines based on the day of the week XRT is initiated.**AZD1775 (MK-1775) Dose Assignment: 95 mg/m²/day* (Dose Level 4)**

BSA (m ²)	Total Daily Dose (mg/day)
0.35-0.39	35
0.40-0.44	40
0.45-0.49	45
0.50-0.55	50
0.56-0.60	55
0.61-0.68	60
0.69-0.76	70
0.77-0.86	75
0.87-0.97	85
0.98-1.10	100
1.11-1.23	110
1.24-1.36	125
1.37-1.49	135
1.50-1.63	150
1.64-1.76	160
1.77-1.97	175
1.98-2.15	200
2.16-2.28	210
2.29- ≥ 2.30	225

*Days 1-5, 8-12, 15-19, 22-26, 29-33, 36-40

Refer to [Appendix V-B](#) for scheduling guidelines based on the day of the week XRT is initiated.

THIS PROTOCOL IS FOR RESEARCH PURPOSES ONLY, SEE PAGE 1 FOR USAGE POLICY

AZD1775 Dose Assignment: 130 mg/m²/dose (Dose Level 5)

BSA (m ²)	AZD1775 Dose (mg/dose)
0.30-0.32	40
0.33-0.36	45
0.37-0.40	50
0.41-0.44	55
0.45-0.51	60
0.52-0.55	70
0.56-0.59	75
0.60-0.63	80
0.64-0.69	85
0.70-0.80	100
0.81-0.88	110
0.89-0.94	120
0.95-1.01	125
1.02-1.09	135
1.10-1.13	145
1.14-1.21	150
1.22-1.26	160
1.27-1.32	170
1.33-1.38	175
1.39-1.48	185
1.49-1.57	200
1.58-1.65	210
1.66-1.71	220
1.72-1.84	225
1.85-2.05	250
2.06-2.21	275
2.22-2.30	300

- For dose reduction due to toxicity, please refer to dose assignment 100 mg/m²/dose below

AZD1775 Dose Assignment: 100 mg/m²/dose

BSA (m ²)	AZD1775 Dose (mg/dose)
0.30-0.32	30
0.33-0.37	35
0.38-0.42	40
0.43-0.47	45
0.48-0.52	50
0.53-0.57	55
0.58-0.67	60
0.68-0.72	70
0.73-0.77	75
0.78-0.82	80
0.83-0.90	85
0.91-1.05	100
1.06-1.15	110

THIS PROTOCOL IS FOR RESEARCH PURPOSES ONLY, SEE PAGE 1 FOR USAGE POLICY

1.16-1.22	120
1.23-1.32	125
1.33-1.42	135
1.43-1.47	145
1.48-1.57	150
1.58-1.65	160
1.66-1.72	170
1.73-1.79	175
1.80-1.92	185
1.93-2.05	200
2.06-2.15	210
2.16-2.22	220
2.23-2.30	225

Refer to [Appendix V-B](#) for scheduling guidelines based on the day of the week XRT is initiated.

AZD1775 Dose Assignment: 160 mg/m²/dose (Dose Level 6)

BSA (m ²)	AZD1775 Dose (mg/dose)
0.30-0.34	50
0.35-0.44	60
0.45-0.52	75
0.53-0.57	85
0.58-0.66	100
0.67-0.73	110
0.74-0.81	125
0.82-0.85	135
0.86-0.91	145
0.92-0.97	150
0.98-1.04	160
1.05-1.17	175
1.18-1.28	200
1.29-1.36	210
1.37-1.51	225
1.52-1.64	250
1.65-1.79	275
1.80-1.95	300
1.96-2.14	325
2.15-2.29	350
2.30	375

Refer to [Appendix V-B](#) for scheduling guidelines based on the day of the week XRT is initiated.

AZD1775 Dose Assignment: 200 mg/m²/dose (Dose Level 7)

BSA (m ²)	AZD1775 Dose (mg/dose)
0.30-0.34	60
0.35-0.39	75
0.40-0.44	85
0.45-0.52	100
0.53-0.57	110

THIS PROTOCOL IS FOR RESEARCH PURPOSES ONLY, SEE PAGE 1 FOR USAGE POLICY

0.58-0.65	125
0.66-0.71	135
0.72-0.81	150
0.82-0.91	175
0.92-1.04	200
1.05-1.17	225
1.18-1.28	250
1.29-1.41	275
1.42-1.58	300
1.59-1.64	325
1.65-1.79	350
1.80-1.93	375
1.94-2.04	400
2.05-2.14	425
2.15-2.29	450
2.30	475

Refer to [Appendix V-B](#) for scheduling guidelines based on the day of the week XRT is initiated.

THIS PROTOCOL IS FOR RESEARCH PURPOSES ONLY, SEE PAGE 1 FOR USAGE POLICY

APPENDIX V-B: GUIDELINES FOR AZD1775 (MK-1775) DOSING SCHEDULE

Please refer to the tables below for scheduling guidelines based on the day of the week XRT is initiated.

Dose Level -1: AZD1775 50 mg/m²/dose daily Mon-Fri QOD, alternating weeks

	Week 1: Days 1-7							Week 2: Days 8-14							Week 3: Days 15-21							Week 4: Days 22-28							Week 5: Days 29-35										
Monday Start Date for XRT																																							
	M	T	W	Th	F	Sa	S	M	T	W	Th	F	Sa	S	M	T	W	Th	F	Sa	S	M	T	W	Th	F	Sa	S	M	T	W	Th	F	Sa	S				
XRT	x	x	x	x	x	-	-	x	x	x	x	x	x	-	-	x	x	x	x	x	x	-	-	x	x	x	x	x	-	-	x	x	x	x	-	-			
AZD1775 50mg/m²	x	-	x	-	x	-	-	-	-	-	-	-	-	-	-	x	-	x	-	x	-	-	-	-	-	-	x	-	x	-	x	-	-	-	-	-			
PK	x	x	x	x	x			x																															
PD	x				x			x																															
Tuesday Start Date for XRT																																							
	T	W	Th	F	Sa	S	M	T	W	Th	F	Sa	S	M	T	W	Th	F	Sa	S	M	T	W	Th	F	Sa	S	M	T	W	Th	F	Sa	S	M				
XRT	x	x	x	x	-	-	x	x	x	x	x	-	-	x	x	x	x	-	-	x	x	x	x	-	-	x	x	x	x	-	-	x	x	x	-	-	x		
AZD1775 50mg/m²	x	-	x	-	-	-	x	-	-	-	-	-	-	-	-	x	-	x	-	x	-	-	-	-	-	-	x	-	x	-	x	-	-	-	-	-			
PK																																							
PD																																							
Wednesday Start Date for XRT																																							
	W	Th	F	Sa	S	M	T	W	Th	F	Sa	S	M	T	W	Th	F	Sa	S	M	T	W	Th	F	Sa	S	M	T	W	Th	F	Sa	S	M	T				
XRT	x	x	x	-	-	x	x	x	x	x	-	-	x	x	x	x	x	-	-	x	x	x	x	-	-	x	x	x	x	-	-	x	x	-	-	x			
AZD1775 50mg/m²	-	-	-	-	-	x	-	x	-	x	-	-	-	-	-	-	-	-	-	x	-	x	-	-	-	-	-	x	-	x	-	x	-	-	-	-			
PK						x	x		x	x			x																										
PD						x			x				x																										
Thursday Start Date for XRT																																							
	Th	F	Sa	S	M	T	W	Th	F	Sa	S	M	T	W	Th	F	Sa	S	M	T	W	Th	F	Sa	S	M	T	W	Th	F	Sa	S	M	T	W				
XRT	x	x	-	-	x	x	x	x	x	x	-	-	x	x	x	x	x	-	-	x	x	x	x	-	-	x	x	x	x	-	-	x	x	-	-	x			
AZD1775 50mg/m²	-	-	-	-	x	-	x	-	x	-	-	-	-	-	-	-	-	-	-	x	-	x	-	-	-	-	-	x	-	x	-	x	-	-	-	-			
PK					x	x		x	x			x																											
PD					x				x				x																										
Friday Start Date for XRT																																							
	F	Sa	S	M	T	W	Th	F	Sa	S	M	T	W	Th	F	Sa	S	M	T	W	Th	F	Sa	S	M	T	W	Th	F	Sa	S	M	T	W	Th				
XRT	x	-	-	x	x	x	x	x	-	-	x	x	x	x	x	-	-	x	x	x	x	x	-	-	x	x	x	x	-	-	x	x	x	-	-	x			
AZD1775 50mg/m²	-	-	-	x	-	x	-	x	-	-	-	-	-	-	-	x	-	x	-	x	-	-	-	-	-	-	x	-	x	-	x	-	-	-	-	-			
PK				x	x		x	x			x																												
PD				x				x				x																											

X = treatment; “-” = no treatment

THIS PROTOCOL IS FOR RESEARCH PURPOSES ONLY, SEE PAGE 1 FOR USAGE POLICY

Dose Level 1: AZD1775 (MK-1775) 50 mg/m²/dose daily Mon-Fri, alternating weeks

“x” = treatment; “-” = no treatment

THIS PROTOCOL IS FOR RESEARCH PURPOSES ONLY, SEE PAGE 1 FOR USAGE POLICY

Dose Level 2: AZD1775 (MK-1775) 50 mg/m² daily Mon-Fri every other week, alternating with weeks of QOD dosing

	Week 1: Days 1-7							Week 2: Days 8-14							Week 3: Days 15-21							Week 4: Days 22-28							Week 5: Days 29-35							Week 6: Days 36-42						
Monday Start Date for XRT	M	T	W	Th	F	Sa	S	M	T	W	Th	F	Sa	S	M	T	W	Th	F	Sa	S	M	T	W	Th	F	Sa	S	M	T	W	Th	F	Sa	S							
XRT	X	X	X	X	X	-	-	X	X	X	X	X	-	-	X	X	X	X	X	-	-	X	X	X	X	X	-	-	X	X	X	X	X	-	-							
AZD1775 50mg/m²	X	X	X	X	X	-	-	X	-	X	-	X	-	-	X	X	X	X	X	-	-	X	-	X	-	X	-	-	X	-	X	-	X	-	-							
PK	X	X		X	X			X																																		
PD	X			X			X																																			
Tuesday Start Date for XRT	T	W	Th	F	Sa	S	M	T	W	Th	F	Sa	S	M	T	W	Th	F	Sa	S	M	T	W	Th	F	Sa	S	M	T	W	Th	F	Sa	S	M							
XRT	X	X	X	X	-	-	X	X	X	X	X	-	-	X	X	X	X	X	-	-	X	X	X	X	X	-	-	X	X	X	X	X	-	-	X							
AZD1775 50mg/m²	-	X	-	X	-	-	X	X	X	X	X	-	-	X	-	X	-	X	-	-	X	X	X	X	X	-	-	X	X	X	X	X	-	-	X							
PK							X	X		X	X			X																												
PD							X			X			X																													
Wednesday Start Date for XRT	W	Th	F	Sa	S	M	T	W	Th	F	Sa	S	M	T	W	Th	F	Sa	S	M	T	W	Th	F	Sa	S	M	T	W	Th	F	Sa	S	M	T							
XRT	X	X	X	-	-	X	X	X	X	X	-	-	X	X	X	X	X	-	-	X	X	X	X	X	-	-	X	X	X	X	X	-	-	X	X							
AZD1775 50mg/m²	X	-	X	-	-	X	X	X	X	X	-	-	X	-	X	-	X	-	-	X	X	X	X	X	-	-	X	X	X	X	X	-	-	X	-							
PK						X	X		X	X			X																													
PD						X			X			X																														
Thursday Start Date for XRT	Th	F	Sa	S	M	T	W	Th	F	Sa	S	M	T	W	Th	F	Sa	S	M	T	W	Th	F	Sa	S	M	T	W	Th	F	Sa	S	M	T								
XRT	X	X	-	-	X	X	X	X	X	-	-	X	X	X	X	X	-	-	X	X	X	X	X	-	-	X	X	X	X	X	-	-	X	X	X							
AZD1775 50mg/m²	-	X	-	-	X	X	X	X	X	-	-	X	-	X	-	X	-	-	X	X	X	X	X	-	-	X	-	X	-	-	X	-	X	-								
PK					X	X		X	X			X			X																											
PD					X			X			X																															
Friday Start Date for XRT	F	Sa	S	M	T	W	Th	F	Sa	S	M	T	W	Th	F	Sa	S	M	T	W	Th	F	Sa	S	M	T	W	Th	F	Sa	S	M	T	W	Th							
XRT	X	-	-	X	X	X	X	X	-	-	X	X	X	X	X	-	-	X	X	X	X	X	-	-	X	X	X	X	X	-	-	X	X	X								
AZD1775 50mg/m²	X	-	-	X	X	X	X	X	-	-	X	-	X	-	X	-	-	X	X	X	X	X	-	-	X	-	X	-	-	X	-	X	-									
PK				X	X		X	X			X			X																												
PD				X			X			X																																

“X” = treatment; “-” = no treatment

THIS PROTOCOL IS FOR RESEARCH PURPOSES ONLY, SEE PAGE 1 FOR USAGE POLICY

Dose Level 3: AZD1775 (MK-1775) 50 mg/m² daily Mon-Fri During Weeks 1-6

	Week 1: Days 1-7							Week 2: Days 8-14							Week 3: Days 15-21							Week 4: Days 22-28							Week 5: Days 29-35								
Monday Start Date for XRT																																					
	M	T	W	Th	F	Sa	S	M	T	W	Th	F	Sa	S	M	T	W	Th	F	Sa	S	M	T	W	Th	F	Sa	S	M	T	W	Th	F	Sa	S		
XRT	X	X	X	X	X	-	-	X	X	X	X	X	-	-	X	X	X	X	X	-	-	X	X	X	X	X	-	-	X	X	X	X	X	-	-		
AZD1775 50mg/m²	X	X	X	X	X	-	-	X	X	X	X	X	-	-	X	X	X	X	X	-	-	X	X	X	X	X	-	-	X	X	X	X	X	-	-		
PK*	X	X		X	X			X																													
PD*	X				X			X																													
Tuesday Start Date for XRT																																					
	T	W	Th	F	Sa	S	M	T	W	Th	F	Sa	S	M	T	W	Th	F	Sa	S	M	T	W	Th	F	Sa	S	M	T	W	Th	F	Sa	S	M		
XRT	X	X	X	X	-	-	X	X	X	X	X	-	-	X	X	X	X	X	-	-	X	X	X	X	X	-	-	X	X	X	X	X	-	-	X		
AZD1775 50mg/m²	X	X	X	X	-	-	X	X	X	X	X	-	-	X	X	X	X	X	-	-	X	X	X	X	X	-	-	X	X	X	X	X	-	-	X		
PK*	B						X	X			X			X																							
PD*	B						X				X			X																							
Wednesday Start Date for XRT																																					
	W	Th	F	Sa	S	M	T	W	Th	F	Sa	S	M	T	W	Th	F	Sa	S	M	T	W	Th	F	Sa	S	M	T	W	Th	F	Sa	S	M	T		
XRT	X	X	X	-	-	X	X	X	X	X	-	-	X	X	X	X	X	-	-	X	X	X	X	X	-	-	X	X	X	X	X	-	-	X	X		
AZD1775 50mg/m²	X	X	X	-	-	X	X	X	X	X	-	-	X	X	X	X	X	-	-	X	X	X	X	X	-	-	X	X	X	X	X	-	-	X	X		
PK*	B					X	X			X			X																								
PD*	B					X				X			X																								
Thursday Start Date for XRT																																					
	Th	F	Sa	S	M	T	W	Th	F	Sa	S	M	T	W	Th	F	Sa	S	M	T	W	Th	F	Sa	S	M	T	W	Th	F	Sa	S	M	T			
XRT	X	X	-	-	X	X	X	X	X	X	-	-	X	X	X	X	X	-	-	X	X	X	X	X	-	-	X	X	X	X	X	-	-	X	X	X	
AZD1775 50mg/m²	X	X	-	-	X	X	X	X	X	X	-	-	X	X	X	X	X	-	-	X	X	X	X	X	-	-	X	X	X	X	X	-	-	X	X	X	
PK*	B				X	X			X			X			X																						
PD*	B				X				X			X			X																						
Friday Start Date for XRT																																					
	F	Sa	S	M	T	W	Th	F	Sa	S	M	T	W	Th	F	Sa	S	M	T	W	Th	F	Sa	S	M	T	W	Th	F	Sa	S	M	T	W	Th		
XRT	X	-	-	X	X	X	X	X	-	-	X	X	X	X	X	-	-	X	X	X	X	X	-	-	X	X	X	X	X	-	-	X	X	X	X		
AZD1775 50mg/m²	X	-	-	X	X	X	X	X	-	-	X	X	X	X	X	-	-	X	X	X	X	X	-	-	X	X	X	X	X	-	-	X	X	X	X		
PK*	B			X	X			X			X			X																							
PD*	B			X				X			X			X																							

"X" = treatment; "-" = no treatment

* B = The initial Baseline/Pre-study blood sample is drawn within 7 days prior to XRT start date. "PK/PD Day 1" is scheduled for the Monday of the first full week of dosing.

THIS PROTOCOL IS FOR RESEARCH PURPOSES ONLY, SEE PAGE 1 FOR USAGE POLICY

Dose Level 4: AZD1775 (MK-1775) 95 mg/m² daily Mon-Fri During Weeks 1-6

	Week 1: Days 1-7							Week 2: Days 8-14							Week 3: Days 15-21							Week 4: Days 22-28							Week 5: Days 29-35								
Monday Start Date for XRT																																					
	M	T	W	Th	F	Sa	S	M	T	W	Th	F	Sa	S	M	T	W	Th	F	Sa	S	M	T	W	Th	F	Sa	S	M	T	W	Th	F	Sa	S		
XRT	X	X	X	X	X	-	-	X	X	X	X	X	-	-	X	X	X	X	X	-	-	X	X	X	X	X	-	-	X	X	X	X	X	-	-		
AZD1775 95mg/m ²	X	X	X	X	X	-	-	X	X	X	X	X	-	-	X	X	X	X	X	-	-	X	X	X	X	X	-	-	X	X	X	X	X	-	-		
PK*	X	X		X		X																															
PD*	X			X			X																														
Tuesday Start Date for XRT																																					
	T	W	Th	F	Sa	S	M	T	W	Th	F	Sa	S	M	T	W	Th	F	Sa	S	M	T	W	Th	F	Sa	S	M	T	W	Th	F	Sa	S	M		
XRT	X	X	X	X	-	-	X	X	X	X	X	-	-	X	X	X	X	X	-	-	X	X	X	X	X	-	-	X	X	X	X	X	-	-	X	-	
AZD1775 95mg/m ²	X	X	X	X	-	-	X	X	X	X	X	-	-	X	X	X	X	X	-	-	X	X	X	X	X	-	-	X	X	X	X	X	-	-	X	-	
PK*	B						X	X			X			X																							
PD*	B						X			X			X																								
Wednesday Start Date for XRT																																					
	W	Th	F	Sa	S	M	T	W	Th	F	Sa	S	M	T	W	Th	F	Sa	S	M	T	W	Th	F	Sa	S	M	T	W	Th	F	Sa	S	M	T		
XRT	X	X	X	-	-	X	X	X	X	X	-	-	X	X	X	X	X	-	-	X	X	X	X	X	-	-	X	X	X	X	X	-	-	X	X		
AZD1775 95mg/m ²	X	X	X	-	-	X	X	X	X	X	-	-	X	X	X	X	X	-	-	X	X	X	X	X	-	-	X	X	X	X	X	-	-	X	X		
PK*	B					X	X			X			X																								
PD*	B					X			X			X																									
Thursday Start Date for XRT																																					
	Th	F	Sa	S	M	T	W	Th	F	Sa	S	M	T	W	Th	F	Sa	S	M	T	W	Th	F	Sa	S	M	T	W	Th	F	Sa	S	M	T			
XRT	X	X	-	-	X	X	X	X	X	-	-	X	X	X	X	X	-	-	X	X	X	X	X	-	-	X	X	X	X	X	-	-	X	X	X		
AZD1775 95mg/m ²	X	X	-	-	X	X	X	X	X	-	-	X	X	X	X	X	-	-	X	X	X	X	X	-	-	X	X	X	X	X	-	-	X	X	X		
PK*	B				X	X			X			X																									
PD*	B				X			X			X																										
Friday Start Date for XRT																																					
	F	Sa	S	M	T	W	Th	F	Sa	S	M	T	W	Th	F	Sa	S	M	T	W	Th	F	Sa	S	M	T	W	Th	F	Sa	S	M	T	W	Th		
XRT	X	-	-	X	X	X	X	X	-	-	X	X	X	X	X	-	-	X	X	X	X	X	-	-	X	X	X	X	X	-	-	X	X	X			
AZD1775 95mg/m ²	X	-	-	X	X	X	X	X	-	-	X	X	X	X	X	-	-	X	X	X	X	X	-	-	X	X	X	X	X	-	-	X	X	X			
PK*	B			X	X			X			X																										
PD*	B			X			X			X																											

"X" = treatment; "-" = no treatment

* B= The initial Baseline/Pre-study blood sample is drawn within 7 days prior to XRT start date. "PK/PD Day 1" is scheduled for the Monday of the first full week

THIS PROTOCOL IS FOR RESEARCH PURPOSES ONLY, SEE PAGE 1 FOR USAGE POLICY

of dosing.

THIS PROTOCOL IS FOR RESEARCH PURPOSES ONLY, SEE PAGE 1 FOR USAGE POLICY

Dose Level 5: AZD1775 (MK-1775) 130 mg/m² Mon-Fri During Weeks 1-6

	Week 1: Days 1-7							Week 2: Days 8-14							Week 3: Days 15-21							Week 4: Days 22-28							Week 5: Days 29-35								
Monday Start Date for XRT																																					
	M	T	W	Th	F	Sa	S	M	T	W	Th	F	Sa	S	M	T	W	Th	F	Sa	S	M	T	W	Th	F	Sa	S	M	T	W	Th	F	Sa	S		
XRT	X	X	X	X	X	-	-	X	X	X	X	X	-	-	X	X	X	X	X	-	-	X	X	X	X	X	-	-	X	X	X	X	X	-	-		
AZD1775 130mg/m²	X	X	X	X	X	-	-	X	X	X	X	X	-	-	X	X	X	X	X	-	-	X	X	X	X	X	-	-	X	X	X	X	X	-	-		
PK*	X	X			X			X																													
PD*	X				X			X																													
Tuesday Start Date for XRT																																					
	T	W	Th	F	Sa	S	M	T	W	Th	F	Sa	S	M	T	W	Th	F	Sa	S	M	T	W	Th	F	Sa	S	M	T	W	Th	F	Sa	S	M		
XRT	X	X	X	X	-	-	X	X	X	X	X	-	-	X	X	X	X	X	-	-	X	X	X	X	X	-	-	X	X	X	X	X	-	-	X		
AZD1775 130mg/m²	X	X	X	X	-	-	X	X	X	X	X	-	-	X	X	X	X	X	-	-	X	X	X	X	X	-	-	X	X	X	X	X	-	-	X		
PK*	B						X	X			X			X																							
PD*	B						X				X			X																							
Wednesday Start Date for XRT																																					
	W	Th	F	Sa	S	M	T	W	Th	F	Sa	S	M	T	W	Th	F	Sa	S	M	T	W	Th	F	Sa	S	M	T	W	Th	F	Sa	S	M	T		
XRT	X	X	X	-	-	X	X	X	X	X	-	-	X	X	X	X	X	-	-	X	X	X	X	X	-	-	X	X	X	X	X	-	-	X	X		
AZD1775 130mg/m²	X	X	X	-	-	X	X	X	X	X	-	-	X	X	X	X	X	-	-	X	X	X	X	X	-	-	X	X	X	X	X	-	-	X	X		
PK*	B					X	X			X			X																								
PD*	B					X				X			X																								
Thursday Start Date for XRT																																					
	Th	F	Sa	S	M	T	W	Th	F	Sa	S	M	T	W	Th	F	Sa	S	M	T	W	Th	F	Sa	S	M	T	W	Th	F	Sa	S	M	T			
XRT	X	X	-	-	X	X	X	X	X	X	-	-	X	X	X	X	X	-	-	X	X	X	X	X	-	-	X	X	X	X	X	-	-	X	X	X	
AZD1775 130mg/m²	X	X	-	-	X	X	X	X	X	X	-	-	X	X	X	X	X	-	-	X	X	X	X	X	-	-	X	X	X	X	X	-	-	X	X	X	
PK*	B				X	X			X			X			X																						
PD*	B				X				X			X			X																						
Friday Start Date for XRT																																					
	F	Sa	S	M	T	W	Th	F	Sa	S	M	T	W	Th	F	Sa	S	M	T	W	Th	F	Sa	S	M	T	W	Th	F	Sa	S	M	T	W	Th		
XRT	X	-	-	X	X	X	X	X	X	-	-	X	X	X	X	X	-	-	X	X	X	X	X	-	-	X	X	X	X	X	-	-	X	X	X		
AZD1775 130mg/m²	X	-	-	X	X	X	X	X	X	-	-	X	X	X	X	X	-	-	X	X	X	X	X	-	-	X	X	X	X	X	-	-	X	X	X		
PK*	B			X	X			X			X			X																							
PD*	B			X				X			X			X																							

"X" = treatment; "-" = no treatment

* B = The initial Baseline/Pre-study blood sample is drawn within 7 days prior to XRT start date. "PK/PD Day 1" is scheduled for the Monday of the first full week of dosing.

THIS PROTOCOL IS FOR RESEARCH PURPOSES ONLY, SEE PAGE 1 FOR USAGE POLICY

Dose Level 6: AZD1775 (MK-1775) 160 mg/m² daily Mon-Fri During Weeks 1-6

	Week 1: Days 1-7							Week 2: Days 8-14							Week 3: Days 15-21							Week 4: Days 22-28							Week 5: Days 29-35							Week 6: Days 36-42						
Monday Start Date for XRT																																										
	M	T	W	Th	F	Sa	S	M	T	W	Th	F	Sa	S	M	T	W	Th	F	Sa	S	M	T	W	Th	F	Sa	S	M	T	W	Th	F	Sa	S							
XRT	X	X	X	X	X	-	-	X	X	X	X	X	-	-	X	X	X	X	X	-	-	X	X	X	X	X	-	-	X	X	X	X	X	-	-							
AZD1775 160mg/m²	X	X	X	X	X	-	-	X	X	X	X	X	-	-	X	X	X	X	X	-	-	X	X	X	X	X	-	-	X	X	X	X	X	-	-							
PK*	X	X			X			X																																		
PD*	X				X			X																																		
Tuesday Start Date for XRT																																										
	T	W	Th	F	Sa	S	M	T	W	Th	F	Sa	S	M	T	W	Th	F	Sa	S	M	T	W	Th	F	Sa	S	M	T	W	Th	F	Sa	S	M							
XRT	X	X	X	X	-	-	X	X	X	X	X	-	-	X	X	X	X	X	-	-	X	X	X	X	X	-	-	X	X	X	X	X	-	-	X							
AZD1775 160mg/m²	X	X	X	X	-	-	X	X	X	X	X	-	-	X	X	X	X	X	-	-	X	X	X	X	X	-	-	X	X	X	X	X	-	-	X							
PK*	B						X	X			X			X																												
PD*	B						X				X			X																												
Wednesday Start Date for XRT																																										
	W	Th	F	Sa	S	M	T	W	Th	F	Sa	S	M	T	W	Th	F	Sa	S	M	T	W	Th	F	Sa	S	M	T	W	Th	F	Sa	S	M	T							
XRT	X	X	X	-	-	X	X	X	X	X	-	-	X	X	X	X	X	-	-	X	X	X	X	X	-	-	X	X	X	X	X	-	-	X	X							
AZD1775 160mg/m²	X	X	X	-	-	X	X	X	X	X	-	-	X	X	X	X	X	-	-	X	X	X	X	X	-	-	X	X	X	X	X	-	-	X	X							
PK*	B					X	X			X			X																													
PD*	B					X				X			X																													
Thursday Start Date for XRT																																										
	Th	F	Sa	S	M	T	W	Th	F	Sa	S	M	T	W	Th	F	Sa	S	M	T	W	Th	F	Sa	S	M	T	W	Th	F	Sa	S	M	T								
XRT	X	X	-	-	X	X	X	X	X	-	-	X	X	X	X	X	-	-	X	X	X	X	X	-	-	X	X	X	X	X	-	-	X	X	X							
AZD1775 160mg/m²	X	X	-	-	X	X	X	X	X	-	-	X	X	X	X	X	-	-	X	X	X	X	X	-	-	X	X	X	X	X	-	-	X	X	X							
PK*	B				X	X			X			X			X																											
PD*	B				X				X			X			X																											
Friday Start Date for XRT																																										
	F	Sa	S	M	T	W	Th	F	Sa	S	M	T	W	Th	F	Sa	S	M	T	W	Th	F	Sa	S	M	T	W	Th	F	Sa	S	M	T	W	Th							
XRT	X	-	-	X	X	X	X	X	-	-	X	X	X	X	X	-	-	X	X	X	X	X	-	-	X	X	X	X	X	-	-	X	X	X								
AZD1775 160mg/m²	X	-	-	X	X	X	X	X	-	-	X	X	X	X	X	-	-	X	X	X	X	X	-	-	X	X	X	X	X	-	-	X	X	X								
PK*	B			X	X			X			X			X																												
PD*	B			X				X			X			X																												

"X" = treatment; "-" = no treatment

* B = The initial Baseline/Pre-study blood sample is drawn within 7 days prior to XRT start date. "PK/PD Day 1" is scheduled for the Monday of the first full week of dosing

THIS PROTOCOL IS FOR RESEARCH PURPOSES ONLY, SEE PAGE 1 FOR USAGE POLICY

Dose Level 7: AZD1775 (MK-1775) 200 mg/m² daily Mon-Fri During Weeks 1-6

	Week 1: Days 1-7							Week 2: Days 8-14							Week 3: Days 15-21							Week 4: Days 22-28							Week 5: Days 29-35							Week 6: Days 36-42						
Monday Start Date for XRT																																										
	M	T	W	Th	F	Sa	S	M	T	W	Th	F	Sa	S	M	T	W	Th	F	Sa	S	M	T	W	Th	F	Sa	S	M	T	W	Th	F	Sa	S							
XRT	X	X	X	X	X	-	-	X	X	X	X	X	-	-	X	X	X	X	X	-	-	X	X	X	X	X	-	-	X	X	X	X	X	-	-							
AZD1775 200mg/m²	X	X	X	X	X	-	-	X	X	X	X	X	-	-	X	X	X	X	X	-	-	X	X	X	X	X	-	-	X	X	X	X	X	-	-							
PK*	X	X			X			X																																		
PD*	X				X			X																																		
Tuesday Start Date for XRT																																										
	T	W	Th	F	Sa	S	M	T	W	Th	F	Sa	S	M	T	W	Th	F	Sa	S	M	T	W	Th	F	Sa	S	M	T	W	Th	F	Sa	S	M							
XRT	X	X	X	X	-	-	X	X	X	X	X	-	-	X	X	X	X	X	-	-	X	X	X	X	X	-	-	X	X	X	X	X	-	-	X							
AZD1775 200mg/m²	X	X	X	X	-	-	X	X	X	X	X	-	-	X	X	X	X	X	-	-	X	X	X	X	X	-	-	X	X	X	X	X	-	-	X							
PK*	B						X	X			X			X																												
PD*	B						X				X			X																												
Wednesday Start Date for XRT																																										
	W	Th	F	Sa	S	M	T	W	Th	F	Sa	S	M	T	W	Th	F	Sa	S	M	T	W	Th	F	Sa	S	M	T	W	Th	F	Sa	S	M	T							
XRT	X	X	X	-	-	X	X	X	X	X	-	-	X	X	X	X	X	-	-	X	X	X	X	X	-	-	X	X	X	X	X	-	-	X	X							
AZD1775 200mg/m²	X	X	X	-	-	X	X	X	X	X	-	-	X	X	X	X	X	-	-	X	X	X	X	X	-	-	X	X	X	X	X	-	-	X	X							
PK*	B					X	X			X			X																													
PD*	B					X				X			X																													
Thursday Start Date for XRT																																										
	Th	F	Sa	S	M	T	W	Th	F	Sa	S	M	T	W	Th	F	Sa	S	M	T	W	Th	F	Sa	S	M	T	W	Th	F	Sa	S	M	T								
XRT	X	X	-	-	X	X	X	X	X	X	-	-	X	X	X	X	X	-	-	X	X	X	X	X	-	-	X	X	X	X	X	-	-	X	X	X						
AZD1775 200mg/m²	X	X	-	-	X	X	X	X	X	X	-	-	X	X	X	X	X	-	-	X	X	X	X	X	-	-	X	X	X	X	X	-	-	X	X	X						
PK*	B				X	X			X			X			X																											
PD*	B				X				X			X			X																											
Friday Start Date for XRT																																										
	F	Sa	S	M	T	W	Th	F	Sa	S	M	T	W	Th	F	Sa	S	M	T	W	Th	F	Sa	S	M	T	W	Th	F	Sa	S	M	T	W	Th							
XRT	X	-	-	X	X	X	X	X	X	-	-	X	X	X	X	X	-	-	X	X	X	X	X	-	-	X	X	X	X	X	-	-	X	X	X							
AZD1775 200mg/m²	X	-	-	X	X	X	X	X	X	-	-	X	X	X	X	X	-	-	X	X	X	X	X	-	-	X	X	X	X	X	-	-	X	X	X							
PK*	B			X	X			X			X			X																												
PD*	B			X				X			X			X																												

"X" = treatment; "-" = no treatment

* B = The initial Baseline/Pre-study blood sample is drawn within 7 days prior to XRT start date. "PK/PD Day 1" is scheduled for the Monday of the first full week of dosing

THIS PROTOCOL IS FOR RESEARCH PURPOSES ONLY, SEE PAGE 1 FOR USAGE POLICY

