8.5.2 Sampling Schedule

Two baseline samples will be collected before the first dose of AZD1775 (MK-1775). Every effort should be made to obtain the baseline (pre-treatment) samples on two different days, if feasible.

Blood samples will also be collected at the time points outlined in [Appendix VIII](#).

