APPENDIX VIII: PHARMACODYNAMIC STUDY FORM

COG Pt ID # _____ ACC # _____ **Day 1 of Protocol Therapy (XRT Start Date):** _____
Please do not write patient names on this form or on samples.

Body Surface Area: _____ m² Dose Level: _____ mg/m² Total Daily Dose: _____ mg

Blood samples will be obtained from all patients (1 ml per time point) prior to treatment start (two baseline samples are required) as well as at the following time points. Every effort should be made to obtain the baseline (pre-treatment) samples on two different days, if feasible. A total of 5 time points for the PD analysis will be collected.

Blood Sample No.	Time Point**	Scheduled Collection Time**	Actual Date Sample Collected	Actual Time Sample Collected (24-hr clock)
1*	Baseline/Pre-study	Within 7 days prior to XRT start date	/ /	_____ :____
2*	Baseline/ PD Day 1	Prior to Monday dose	/ /	_____ :____
AZD1775 (MK-1775) Dose on PD Day 1**		Date: ____ / ____ / ____	Time: ____ ____ : ____ ____	
3	PD Day 1	6-8 hr after Monday dose	/ /	_____ :____
AZD1775 (MK-1775) Dose on PD Day 5**		Date: ____ / ____ / ____	Time: ____ ____ : ____ ____	
4	PD Day 5	6-8 hr after Friday dose	/ /	_____ :____
5	PD Day 8	Prior to Monday dose	/ /	_____ :____
AZD1775 (MK-1775) Dose on PD Day 8**		Date: ____ / ____ / ____	Time: ____ ____ : ____ ____	

*Baseline samples should be taken at least 1 day apart, if feasible.

**Refer to [Appendix V-B](#) for PD collection based on XRT start date.

One copy of this Pharmacodynamic Study Form should be uploaded into RAVE. A second copy should be sent with the samples to the address listed in [Section 8.5.5](#). See [Section 8.5](#) for detailed guidelines for packaging and shipping PD samples.

Record any notes for Sample Storage Conditions below.

Notes:

If this form will be used as a source document, the site personnel who collected the samples must sign and date this form below:

Signature: _____
(site personnel who collected samples)

Date: _____

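### At dose levels 3–7, the second PD baseline for Tuesday–Friday radiation starts is scheduled after AZD1775 dosing has begun, in conflict with section 8.5.2 and the Appendix VIII introduction

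*Combined protocol and SAP*

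**What the plan says.** Section 8.5.1 takes two baseline samples per patient, computes the within-patient SD from them, and treats a change of 2 SD as significant. Section 8.5.2 sets their timing: "Two baseline samples will be collected before the first dose of AZD1775 (MK-1775"). It also asks sites to try to take the "samples on two different days, if feasible". The introduction to Appendix VIII has blood drawn "prior to treatment start (two baseline samples are required").

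The Appendix VIII form then fixes the two draws. Sample 1 is a pre-study draw in the week before radiation begins. Sample 2 is labelled "Baseline/ PD Day 1" and timed "Prior to Monday dose".

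Appendix V-B gives the calendar. For dose levels 3–7 a footnote says that PK/PD Day 1 "is scheduled for the Monday of the first full week of dosing". The mark B in those grids stands for the initial pre-study sample only. Section 5.1 recommends a Monday start but does not require it, and Appendix V-B has grids for all five weekdays.

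Section 11.5 compares the markers before and after AZD1775 with paired methods and calls these analyses descriptive and exploratory.

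**The concern.** A patient who starts radiation on a Tuesday to Friday at levels 3–7 also starts AZD1775 that day. The Monday of the first full week is then not a pre-treatment day, although the form calls the sample drawn on it a baseline. The same form takes sample 5 before the dose on the Monday of PD Day 8 and does not call it baseline. In a Monday starter that sample follows five doses and a weekend; a Tuesday starter's sample 2 follows four doses and a weekend.

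What is at stake is the noise estimate and the reference value for p-CDC2, p-HH3 and γ-H2AX. Section 8.5.1 expects drug and radiation to move these markers, γ-H2AX being a marker of DNA double-strand breaks. Any effect left in the Monday sample would therefore lie in the direction the trial is trying to detect. It would widen the SD and, if the two samples are averaged, pull the baseline toward the on-treatment value.

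**Working it through.** **1. The plan's own figure.** Section 8.5.2 requires 2 baselines before the first dose.

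**2. Count from the calendar.** Inputs are the radiation and AZD1775 rows of the Appendix V-B grids for levels 3–7, and the first PD mark after B, which falls on the Monday of the first full week. Doses before sample 2 are the AZD1775 marks before that Monday.

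| Radiation start | AZD1775 days before that Monday | Doses before sample 2 | Fractions before sample 2 (at least) | Baselines before first dose |
|---|---|---|---|---|
| Monday | none | 0 | 0 | 2 |
| Tuesday | Tue, Wed, Thu, Fri | 4 | 4 | 1 |
| Wednesday | Wed, Thu, Fri | 3 | 3 | 1 |
| Thursday | Thu, Fri | 2 | 2 | 1 |
| Friday | Fri | 1 | 1 | 1 |

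The required 2 is reproduced only for Monday starts.

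**3. Does other text supply the missing sample?** B does not, since the footnote defines it as sample 1. The feasibility clause in 8.5.2 does not, since it covers only drawing on different days. Reading treatment start in Appendix VIII as either radiation or drug does not help, because sample 2 follows both.

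**4. Consequence for the 2-SD rule.** The SD from two baselines b1 and b2 is s = |b1 − b2|/√2. With one valid baseline there are 0 degrees of freedom and no SD, whatever the carry-over.

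**5. Illustration if the Monday value is used anyway.** These inputs are assumptions; the documents give neither. Within-patient SD is 1, the true effect is d = 3, and a share c of it remains in b2. Then b1 − b2 has mean −dc and variance 2, so

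- E[s²] = (2 + (dc)²)/2 = 1 + (dc)²/2;
- mean change from the two-sample mean = d(1 − c/2);
- mean change from sample 1 = d.

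For example, at c = 0.5: √(1 + 1.5²/2) = √2.125 = 1.46, and 3 × 0.75 = 2.25, which is 75% of 3. The flag rates come from a simulation of 2,000,000 draws with b1 ~ N(0,1), b2 ~ N(3c,1) and y ~ N(3,1), flagging when |y − reference| > 2s. Section 8.5.1 does not say which reference applies, so both are shown.

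| c | Root-mean-square SD | Change kept, from mean | Change kept, from sample 1 | Flagged, from mean | Flagged, from sample 1 |
|---|---|---|---|---|---|
| 0 | 1.00 | 100% | 100% | 80% | 80% |
| 0.1 | 1.02 | 95% | 100% | 77% | 80.5% |
| 0.25 | 1.13 | 88% | 100% | 69% | 78% |
| 0.5 | 1.46 | 75% | 100% | 50% | 65% |
| 1 | 2.35 | 50% | 100% | 12% | 24% |

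At small c the loss is slight or nil; at large c it is severe. These are not power figures. With no effect at all and perfectly timed baselines, the rule flags 35% (from the mean) or 38% (from sample 1), because an SD from two values is so unstable.

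**The case against.** The strongest reply is that section 8.5.2 and the Appendix VIII introduction bind for every start day, so a site that obeys them draws both samples in time. The documents then show conflicting instructions, not missing data. This stands. A reader might infer that every Tuesday–Friday starter has only one valid baseline, but that treats the calendar as a record of what was done. It holds only for sites that followed the calendar.

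Second, the consequence is small. The analyses are exploratory, a Monday start is recommended, section 11.5 does not require the baselines to be averaged, and change from sample 1 alone is unbiased by this fault. All of that stands and limits the point. It does not restore the 2-SD rule, which needs two pre-treatment values.

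Third, the illustration has no source in the documents for d or c. That is also true. The trial's own PD Day 8 sample in Monday starters, taken after a weekend, bears on c, and the effect could prove negligible.

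Fourth, a reader might extend the count. Drug follows that day's fraction (section 9.1.5), so the Monday draw could follow one further fraction, and a Monday starter's sample 2 could follow one. The protocol does not order the blood draw against the fraction, so these are possibilities only. Nor is the fault shown at every level. The level 2 grid, headed "daily Mon-Fri every other week, alternating with weeks of QOD dosing", has no such footnote and is partly shifted in the text reviewed; it probably gives 2, 2, 1 and 1 doses. The level 1 grid could not be read there. At level −1 the drug is held until the Monday for Wednesday–Friday starts.

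**Conclusion.** The conflict is certain for dose levels 3–7 and non-Monday starts, and the counts of 4, 3, 2 and 1 scheduled doses are exact. They assume that the grid is followed with no missed days. Where a site followed the calendar, the per-patient SD and 2-SD flag have no valid basis in these patients.

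The size of the distortion is unknown. The share of patients affected could be anything from 0 to 100%, and weekend recovery of the markers is not stated. The tabulated losses only show how the answer depends on carry-over.

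A reader might infer that the dose finding is compromised. The documents do not support this: DLT, MTD and escalation do not use the PD markers. A reader might also expect better timing to cure the rule's high false-flag rate. It would not, since that rate arises with two clean baselines as well and is a separate matter. The point is worth correcting because the plan contradicts itself on an input to its own analysis rule.

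**What to change.** Reconcile section 8.5.2, Appendix VIII and Appendix V-B so that both PD baselines are drawn before the first AZD1775 dose and before treatment start, whatever the weekday. In Tuesday–Friday starters, label the pre-dose sample on the Monday of the first full week as on-treatment.

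For samples already collected, use the sample dates, dose times and radiation start date on the Appendix VIII form to identify baselines drawn after dosing began. Exclude these from the baseline mean and SD. Report those patients' change from sample 1, without the individual 2-SD flag.

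The cost is some appendix wording and one 1 mL draw moved earlier. If the Monday sample is kept and a draw is added, the PD total becomes 5 + 1 = 6 mL, against 5 mL in Appendix VI. The earlier draw may mean a separate pre-treatment blood draw in a child. Fewer past patients will have an SD of their own.
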